1.1.9 Functional and Clinical Outcome Measurements

Healing of the injury will be clinically monitored using repeated functional measurements, pain assessments and by means of standardized questionnaires. The follow-up will be performed according to table 2. The functional examinations will include the supination and pronation of the forearm, flexion and extension of elbow, dorsiflexion and palmar flexion of the wrist using a goniometer, and their comparison to the corresponding measurements of the subject's healthy forearm.

[figure not shown]

Figure 1 Determination of forearm's pronation and supination angles

In measuring of pronation, the vertical limb of the goniometer is placed parallel to the long axis of the humerus, while the horizontal limb is placed on the back of the wrist (to eliminate additional motion at the radiocarpal joint). In the measuring supination the horizontal limb is placed on the anterior aspect. The average range of pronation/supination is 90/90 degrees (50/50 degrees necessary for activities of daily living). ***Flynn's criteria for elbow assessment is used to evaluate the clinical significance of outcomes (excellent and good comprising satisfactory, and fair and poor comprising unsatisfactory), as well as the classification by Price.***

[figure not shown]

Figure 2 Determination of A) elbow's flexion and extension, B) wrist's dorsiflexion and palmar flexion

Clinical outcome and fracture union will be also assessed by the absence of pain and bony tenderness at fracture site. The subjects will be also asked to perform self-assessment of perceived pain in the region of study using 10 cm visual analogue scale (VAS) as a measure of pain severity.

1.1.10 Radiographic Evaluations

This study will involve normal repeated radiographic examinations of the forearm for assessment of outcome, progress of fracture union and also possible development of complications related to injury or treatment.

Plain Radiographs

The plain radiographs in standard anteroposterior (AP) and lateral projections will be taken before and after surgery, followed by repeated radiographs according to table 2.

The parameters defined from forearm's plain radiographs are

- fracture reduction and retention
- fracture angulation
- fracture union as bridging callus by the presence of obliteration of fracture lines (union, delayed union, non-union)
- increased/decreased radial bow (fracture malunion)
- limb-length discrepancy
- complications related to injury or treatment (implant-related osteolysis)

Clinical Investigation Plan

Bioabsorbable Intramedullary Nail Fixation of Forearm Fractures in Children

The angulation of the fractures will be measured on anteroposterior and lateral radiographic views. Radiographic union will be defined as the presence of bridging callus at all visualized cortices on the anteroposterior and lateral radiographic views. Delayed union will be classified as incomplete healing at 10 weeks in children <9 years of age and at 12 weeks in children ≥9 years of age. [23]

At latest follow-up malunion will be quantified by measurement of the amount and location of the maximum radial bow in relation to the contralateral, normal forearm as described by Schemitsch and Richards. The radial bow will be measured on the anteroposterior radiograph of the forearm, which includes the wrist and elbow joints.

Limb-length discrepancy will be assessed by measurement of the distances between lateral epicondyle of the humerus and radial styloid process in both limbs.

MR Imaging

The parameters defined from forearm's MR images are

- fracture reduction and retention
- fracture angulation
- fracture union as bridging callus by the presence of obliteration of fracture lines (union, delayed union, non-union)
- fracture malunion (radial bow, Limb-length discrepancy)
- complications related to injury or treatment (implant related osteolysis and detection of IM nail failure)
- soft-tissue reactions (oedema, abnormal fibrotic tissue, post-traumatic calcification) in the surroundings
- bioabsorption of the investigational device

Evaluation of Variables

The following variables will be measured from each subject at designed visits in evaluation of the efficacy and safety of fixation. The radiographic measurements are performed by an experienced paediatric radiologist, familiar with children's trauma.

1.1.11 Primary Performance Variable

Evaluation of functional and clinical outcome consists of following determinations:

Clinical Investigation Plan

Bioabsorbable Intramedullary Nail Fixation of Forearm Fractures in Children

- Measurements of the range of motion (ROM) in the forearm, expressed as degrees \pm SD
 - Loss of supination and pronation of the forearm (graded according to the table below),
 - Loss of flexion and extension of elbow and
 - Loss of dorsiflexion and palmar flexion of the wrist, graded according to the Flynn's criteria (<10 degrees of change are excellent or good i.e. satisfactory; >10 degrees of change are fair or poor i.e. unsatisfactory); and Price's classification.
- General pain and pain at fracture site assessed by VAS, expressed as mm \pm SD
 - Duration of post-operative medication for pain

Table 1 Classification of outcome, graded using a system described by Price [25]

Outcome	Loss of Forearm Rotation and Symptoms
Excellent	$\leq 15^\circ$ loss of forearm rotation and no complaints with strenuous activity
Good	A loss of forearm rotation of 15° to 30° and only mild complaints with strenuous physical activity
Fair	A loss of forearm rotation of 30° to 90° and mild complaints during activities of daily living
Poor	All other outcomes

1.1.12 Secondary Variables

Forearm's plain radiographs in AP and lateral projections and MRI imaging will be used to determine:

- Fracture reduction and retention
- Fracture angulation, expressed as degrees \pm SD (graded according to Table below)
- Bony union formation and rate (union, delayed union, non-union, malunion)

1.1.13 Safety Variables

Incidence of adverse events (AE) and serious adverse event (SAE) will be expressed as proportion per group. These consist of e.g. complications related to injury or treatment and will be separated into resolved versus long-term or non-resolved complications, which included a need for return to the operating room. Monitored AE's are:

Clinical Investigation Plan

Bioabsorbable Intramedullary Nail Fixation of Forearm Fractures in Children

- Fracture delayed union, nonunion and malunion
- Incidence of infection
- Intra-operative complications related to fixation hardware
- Need for secondary reduction due to fracture instability
- Osteolysis
- Biocompatibility reactions
- Mechanical implant failure

The potential drop-outs by any reason are recognized and reported, despite the lack of 2-year follow-up data, whilst no comparisons at end-point are available.

1.1.14 Other Variables

Other variables documented in CRF are:

- Operation time
- Number of days lost from usual activities
 - Parents lost working days
- Length of hospitalization stay
- Complaints in daily living
- Esthetics

Statistics

Recommended statistical methods will be applied. All deviations made after approval of the CIP will be described and justified in the final study report.

Sample Size Considerations

Primary outcome variable in this study is loss of supination and pronation within 6, 12, 26, 52, and 104 weeks after surgery. The non-inferiority margin is set to be 80 % in the calculations (=Power).

It is previously known that the forearm pronation in this age group is 81.2 degrees (95% CI 79.6-82.28) and 79.6 degrees (95% CI 78.8-80.4) in girls and boys, respectively. The corresponding supination archs are 90.0 degrees (95% CI 88.0-92.0) and 87.8 degrees (95% CI 85.7-89.9). [26] The standard deviation (SD) is 6.1 degrees in pronation and 7.6 degrees in supination. We determined that the new method (ActivaNail –intramedullary fixation) should

Clinical Investigation Plan

Bioabsorbable Intramedullary Nail Fixation of Forearm Fractures in Children

result to the forearm rotational range of motion that is not more than 15 degrees lower, compared to the rotational range of motion in TEN group, according to the Price's classification (<15 degrees of decrease refers to excellent outcome).

Difference between means in the groups is set as 7.0 and the Alpha as 0.05. The sample size is estimated to be 13 experimental subjects and 13 controls according to an unpaired two sample Student t test. This study population will also be exclusively large enough to recognize decrease in the ROM that is clinically significant (>15 degrees of decrease in supination or pronation in ActivaNail compared to TEN group).

Statistical Hypothesis

The following hypothesis will be tested for the primary efficacy variable:

H₀: Investigational device is inferior to comparative devices

H₁: Investigational device is non-inferior to comparative devices

The non-inferiority limit is set to 80 %. Thus, non-inferiority is shown if the upper limit of the 95% confidence interval for the difference is less than or equal to 5 %.

Statistical Methods

All operated subjects who reach the 2-year follow-up will be included in the statistical analysis. Study data will be tabulated by treatment groups with descriptive summary statistics.

The conventional level of 5% will be considered the level of statistical significance. All tests will be two-sided. Accordingly, 95% confidence intervals will be used.

Normality assumptions will be checked using normal probability plot for residuals. The use of transformation for a particular variable will be decided after examining the assumptions with the original scale of measurement. Analysis may be repeated without possible outliers.

The primary variable will be analyzed using an analysis of variance model for repeated measurements. Treatment differences with 95% confidence intervals will be calculated from the model. If the assumptions for the parametric models are not met suitable non-parametric models will be used.

Clinical Investigation Plan

Bioabsorbable Intramedullary Nail Fixation of Forearm Fractures in Children

Adverse Events

The safety variables to be evaluated include adverse events (AE), findings from physical and radiographic examinations, subjective reports of pain and functional outcome assessments. Further, all drop-outs will be reported. The adverse event data will include the following displays:

- AEs categorized by body system
- AEs categorized by severity grades 1-4 (mild, moderate, severe, life-threatening)
- AEs involving the region under study (RUS) specifically:
 - Fracture delayed union, nonunion and malunion
 - Hardware failure
 - Infection

All Serious Adverse Events (SAE) will be reported within 24 hours to the Sponsor. The SAEs include death, life-threatening event, medically important event, device malfunction, hospitalization, accidental exposure, persistent disability or incapacity, and cancer. In emergency SAE cases, the patients are requested to seek help in the Emergency room of the University Central Hospital. Any adverse events and their effects are reported using Case Report Form (CRF).

Quality Management

Monitoring Arrangements

The sponsor is responsible for the monitoring of this study. The principal investigator will provide sponsor with the data recorded during the study without personal identification data to allow the sponsor to check the compliance of the study with the CIP. The sponsor will appoint a monitor for assessing the investigator's compliance with the Clinical Investigation Plan and for performing source-data verification. A monitoring plan and report will be prepared.

Data Management

The study data of the CRFs will be stored at the research sites and copies without personal identification data will be sent to the sponsor for storing.

Clinical Investigation Plan

Bioabsorbable Intramedullary Nail Fixation of Forearm Fractures in Children

Quality Assurance

Bioretec has a certified Quality Management System according to ISO 13485:2003. Investigational devices will be tested according to SOP's of the Bioretec Ltd using the test equipment maintained and calibrated according to relevant SOP's of Bioretec Ltd.

Discontinuation and Withdrawal of Subjects

A subject may be discontinued (withdrawn) from the study at any time if the subject or the investigator believes it is not in the best interest of the subject to continue participation in the study. Subjects withdrawn from the study will not be replaced, regardless of the reason for withdrawal. All study data provided up to the time of withdrawal will be collected and reported. This information will be recorded in the subject's source documentation and in the CRF. Subjects who discontinue their participation or are withdrawn from the trial will be asked to participate in a final study visit at 104-week follow-up visit.

Termination of the Study

The sponsor may terminate individual subject or group of subjects, or the entire investigation, at any time for any of the following reasons:

- Failure to enrol subjects
- Protocol violations
- Inaccurate or incomplete data
- Unsafe or unethical practices
- Questionable safety of the test device
- Suspected lack of efficacy of the test device
- Administrative decision.

If the investigator terminates the study prematurely, the investigator provides the ethical committee and the sponsor with a written statement describing why the study was terminated prematurely. Prompt compliance with this requirement is essential so that the sponsor may comply with its regulatory obligations.

Clinical Investigation Plan

Bioabsorbable Intramedullary Nail Fixation of Forearm Fractures in Children

CIP Amendments and Deviations

All amendments to the CIP with the justifications will be agreed and recorded between sponsor and the principal investigator. Any deviation to this clinical investigation plan made by investigators shall be recorded with an explanation for deviation and reported to sponsor. The significance of deviation will be determined by sponsor. When appropriate, Ethical Committee and other appropriate regulatory bodies are informed.

Publication Policy

If on completion of the study the data warrants publication, the investigator may publish the results in recognized (refereed) scientific journals. The investigator shall submit reports, abstracts, or manuscripts to the sponsor for review prior submission for publication or presentation. The sponsor shall have 60 days to respond with any requested revisions, including without limitation, the deletion of confidential information. The principal investigator shall act in good faith upon requested revisions. The principal investigator shall delay submission of such publication or presentation materials for up to 90 days in order to have a patent application(s) filed.

Subject Injury

In general, if a subject is injured as direct result of the test device, the sponsor will pay for the reasonable and necessary medical treatment for the injury, to the extent the expenses are not covered by the subject's medical insurance, a government program, or other responsible third party.

Report Forms

Case report forms (CRF) are records of data of each subject as defined by the CIP. Data to be collected in this study will be entered on CRFs. All data recorded is recommended to be verifiable in hospital or patient records. The CRFs are required for each study subject. The investigator should confirm the content CRF by signing and dating the applicable pages. Original completed forms will be maintained by the principal investigator. A copy of each CRF without personal identification will be sent to sponsor.

Clinical Investigation Plan

Bioabsorbable Intramedullary Nail Fixation of Forearm Fractures in Children

References

1. Koval K.J. and Zuckerman J.D., *Handbook of Fractures*, 3rd ed. [2006], p. 540.
2. *Campbell's Operative Orthopaedics*, 10th ed., [2003], vol 2, p. 1405.
3. Noonan K.I. and Price C.T., *J. Am. Acad. Orthop. Surg.*, 6 [1998] 146.
8. Carmichael K.D. and English C., *Orthopedics*, 30 [2007] 379.

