- [name], Chief Paediatric Radiologist

Central Hospital of Päijät-Häme, Department of Surgery

[name]

- [name], PhD, Orthopaedic Surgeon

Clinical Investigation Plan

Bioabsorbable Intramedullary Nail Fixation of Forearm Fractures in Children

Synopsis

Name of Sponsor: Bioretec Ltd.
Name of Medical Device: Bioabsorbable Intramedullary Nail
Title of Study: Bioabsorbable Intramedullary Nail Fixation of Forearm Fractures in Children
Investigators: 
○ [name], PhD, Associate Professor, Paediatric Surgeon○ [name], PhD, Orthopaedic Surgeon○ [name], Statistician○ [name], MB, PhD candidate○ [name], Paediatric Radiologist○ [name], Professor, MD, PhD, Paediatric Orthopedist and Surgeon○ [name], [name], PhD, Paediatric Orthopedist and Surgeon
Study Centres: 
- Oulu University Hospital, Department of Children and Adolescents- Central Hospital of Päijät-Häme, Department of Surgery, Unit of Paediatric Surgery
Studied Period (weeks): 52 (follow up 2 years) Date of First Enrolment: 2010 Date of Last Completed: 2018
Objectives: 
Primary objective: Clinical outcome of the fracture treatment is equal between patients treated by the new bioabsorbable medical device and by standard of care using a titanium alloy device. This will be assessed by functional and clinical outcome measuring range of motion of forearm, wrist and elbow and pain assessment at two-years' follow-up.
 
Secondary objective: The new medical device (bioabsorbable intramedullary nail) is at least as good as the routinely used device (elastic stable titanium alloy intramedullary nail) in forearm fracture treatment to achieve a level of reduction and stabilisation that is appropriate to the age of the child. This will be assessed by radiological outcome and determination of bony union formation and alignment in the healing forearm fracture using radiographic methods; further, soft-tissue and bone-tissue reactions are to be evaluated by MRI.

Methodology:

Clinical Investigation Plan

Bioabsorbable Intramedullary Nail Fixation of Forearm Fractures in Children

The fracture is fixed using the new medical device (bioabsorbable intramedullary nail) or the standard titanium intramedullary nail.

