1.1.7 Visit Schedule

For each subject, the study consists of assessments preoperatively, immediately after operation and the follow up visits postoperatively. The recommend time window of scheduled visits is ± 7 days. The clinical assessments and procedures performed at each visit are shown in Table 2.

Clinical Investigation Plan

Bioabsorbable Intramedullary Nail Fixation of Forearm Fractures in Children

During these visits will be investigated: function of both arms, radiological fracture healing, well-being and incidence of complications.

Table 2 Assessment and procedures at each visit

Assessment	Operation		4 week	12 weeks	26 weeks	52 weeks	104 weeks
	Pre-operative	Post-operative					
	Visit 1	Visit 2	Visit 3	Visit 4	Visit 5	Call 6	Visit 7
Informed consent, inclusion and exclusion criteria	X						
Demographics, medical history	X						
Injuries and comorbidities	X						
Randomization	X						
Fracture reduction and fixation	X						
Cast removal			X				
TEN nail removal					X		
Primary performance variable	Operation		4 week	12 weeks	26 weeks	52 weeks	104 weeks
	Pre-operative	Post-operative					
	Visit 1	Visit 2	Visit 3	Visit 4	Visit 5	Call 6	Visit 7
Functional and clinical outcome evaluated by measuring rate of motion			X	X	X		X
Pain assessment		X	X	X	X	X	X
Subjective		X	X	X	X	X	X

Clinical Investigation Plan

Bioabsorbable Intramedullary Nail Fixation of Forearm Fractures in Children

result							
Secondary variables	Operation		4 week	12 weeks	26 weeks	52 weeks	104 weeks
	Pre-operative	Post-operative					
	Visit 1	Visit 2	Visit 3	Visit 4	Visit 5	Call 6	Visit 7
Radiographic outcome and bone union formation evaluated by plain radiographs	X	X	X	X	X		X
Radiographic outcome and bone union formation evaluated by MRI imaging		X*		X*		X*	X*
Safety and tolerability variables	Operation		4 week	12 weeks	26 weeks	52 weeks	104 weeks
	Pre-operative	Post-operative					
	Visit 1	Visit 2	Visit 3	Visit 4	Visit 5	Call 6	Visit 7
Adverse events	X	X	X	X	X	X	X
Concomitant medications	X	X	X	X	X	X	X
Conclusion of participation							X

* Radiographic outcome and bone union formation of 5-10 subjects will be evaluated by MRI imaging immediately after operation and three follow up visits

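### The primary outcome is defined at week 52, when no range of motion is measured, and the non-inferiority rule names no visit although the primary objective is set at two years.

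*Protocol*

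**What the plan says.** The protocol describes the timing of the primary outcome in several places.

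- **Section 10.1, Sample Size Considerations:** "Primary outcome variable in this study is loss of supination and pronation within 6, 12, 26, 52, and 104 weeks after surgery".
- **Visit Schedule, Table 2:** the row "Functional and clinical outcome evaluated by measuring rate of motion" is marked at weeks 4, 12, 26 and 104. The week-52 column is headed as a call, not a visit. Pain and subjective result are marked there; range of motion is blank. There is no week-6 column.
- **Functional and Clinical Outcome Measurements:** "The follow-up will be performed according to table 2. The functional examinations will include the supination and pronation of the forearm". The measurement uses a goniometer and is compared with the healthy arm.
- **Synopsis, primary objective:** the assessment is of "range of motion of forearm, wrist and elbow and pain assessment at two-years' follow-up".
- **Section 10.2, Statistical Hypothesis:** "non-inferiority is shown if the upper limit of the 95% confidence interval for the difference is less than or equal to 5" (the unit given is per cent). No visit is named.
- **Section 10.3, Statistical Methods:** "All operated subjects who reach the 2-year follow-up will be included in the statistical analysis". The primary variable goes into a repeated-measures analysis of variance, from which treatment differences and 95% intervals are taken. No visit or contrast is named.

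Two further places point to two years. Under Safety Variables, drop-outs without 2-year data are to be reported "whilst no comparisons at end-point are available". Under section 13, withdrawn subjects "will be asked to participate in a final study visit at 104-week follow-up visit".

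**The concern.** There are two linked faults. First, the primary outcome includes a time at which the protocol collects no data. Second, the objective asks a two-year question, the outcome is spread over five times, and the decision rule rests on one difference whose time is not stated.

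The difference set against the margin decides the trial. If it is an average over visits, most of the weight falls at or before week 26. A deficit that persists or appears late is then diluted, which in a non-inferiority trial favours the test device. The opposite can also happen: an early deficit that has resolved by two years would count against the device.

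**Working it through.** **1. Listed times against scheduled measurements**

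| Week | Listed in 10.1 | Range of motion in Table 2 |
|---|---|---|
| 4 | no | yes |
| 6 | yes | no such visit |
| 12 | yes | yes |
| 26 | yes | yes |
| 52 | yes | no (call) |
| 104 | yes | yes |

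The visit window is ±7 days, so the week-4 visit covers weeks 3 to 5. It matches the week-6 entry only if 10.1 is read as meaning any time up to week 6. Week 52 cannot be rescued that way: the only range-of-motion measurement after week 26 is at week 104.

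**2. The plan's own sample size**

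A two-sided unpaired t test with difference 7.0, SD 6.1 (pronation), alpha 0.05 and power 80% needs 12.96, so 13 per group (power at 13 is 80.1%). The stated figure is reproduced, and it is for one comparison at one unnamed time.

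**3. What the choice of difference does**

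Inputs from section 10.1: 13 per group, SD 6.1 and 7.6 degrees, limit M = 15 degrees. Alternative limit from section 8.1: M = 10 degrees. Assumed: between-visit correlation ρ of 0.3 to 0.7, the same SD and correlation at all visits, equal visit weights, and the time courses below.

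The rule is that the upper 95% limit of the difference (test minus control loss) is at or below M, with 24 degrees of freedom and t = 2.064.

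- Standard error at week 104: SD × √(2/13) = 2.393 (SD 6.1) or 2.981 (SD 7.6).
- Standard error of the four-visit mean: that value × √((1 + 3ρ)/4).
- With true deficit M at week 104 and f × M at weeks 4, 12 and 26, the true four-visit mean is M(3f + 1)/4. For M = 15 and f = 0 this is 15/4 = 3.75. For f = 0.5 it is 15 × 2.5/4 = 9.375.

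Probability of passing, from the noncentral t distribution:

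| M | f | True mean | SD 6.1, ρ 0.3 / 0.5 / 0.7 | SD 7.6, ρ 0.3 / 0.5 / 0.7 |
|---|---|---|---|---|
| 15 | 0 | 3.75 | 1.000 / 1.000 / 0.999 | 0.999 / 0.996 / 0.984 |
| 15 | 0.5 | 9.375 | 0.905 / 0.814 / 0.727 | 0.748 / 0.630 / 0.539 |
| 10 | 0 | 2.5 | 0.992 / 0.967 / 0.927 | 0.938 / 0.863 / 0.783 |
| 10 | 0.5 | 6.25 | 0.588 / 0.477 / 0.401 | 0.418 / 0.333 / 0.278 |

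The week-104 comparison passes with probability 0.025 in every row, because its true deficit sits exactly at the limit.

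**4. The reverse pattern**

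Take 15 degrees at weeks 4, 12 and 26, none at week 104, and M = 15. The true mean is 45/4 = 11.25. The average passes with probability 0.588 / 0.477 / 0.401 (SD 6.1) and 0.418 / 0.333 / 0.278 (SD 7.6). The week-104 comparison passes with 1.000 and 0.998.

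**5. Precision given up by using week 104**

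The interval width ratio, week 104 to four-visit mean, is 1/√((1 + 3ρ)/4) = 1.45, 1.26 and 1.14 at ρ = 0.3, 0.5 and 0.7.

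**The case against.** The week-52 mismatch is not in dispute. The case on the other side concerns the rest.

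- **No passage prescribes an average.** Section 10.3 speaks of treatment differences in the plural, which suits visit-by-visit estimates. This is fair, but the plural still does not say which difference decides.
- **The four-visit average includes week 4, which 10.1 does not list.** Only weeks 12, 26 and 104 are both listed and measured. Averaging those three gives week 104 a weight of 33% instead of 25%. For M = 15 the pass probabilities become 95% to over 99.9% (no earlier deficit) and 44 to 78% (half). For M = 10 they become 67 to 96% and 22 to 45%. The reverse pattern passes in 44 to 78%, and the week-104 interval is 12 to 37% wider than the average's. The ranges move; the direction does not.
- **The illustration is loosely anchored.** The SDs stand beside reference values, not loss of motion after fracture, and neither 15 nor 10 degrees is the limit written in 10.2. This stands: the figures show what is possible and do not predict this trial.
- **Only the synopsis states two years for the primary objective.** Section 8.1 gives no time. The analysis set, drop-out and withdrawal passages concern which subjects are analysed or recalled, not the time of the comparison. Week 104 is therefore the best-supported reading, not an explicit rule.
- **The choice of contrast is often left to the SAP.** Here, though, the protocol itself fixes the objective, outcome times, rule and model, and they disagree. An SAP could not follow both 10.1 and the synopsis.
- **Week 6 is arguable,** on the loose reading described above.

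**Conclusion.** The concern holds. One of the five listed times (week 52) has no planned data, a second (week 6) is arguable, and one of the four measured visits (week 4) is not listed. The deciding difference is tied to no visit, while the synopsis asks about two years.

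With equal weights over the four measured visits, week 104 counts for 25%, so a 15-degree deficit present only then shrinks to 3.75 degrees. At the 15-degree limit, a device that the two-year comparison would pass in 2.5% of trials passes on the average in 98% to over 99.9% or in 54 to 91%, depending on the earlier course. At 10 degrees the ranges are 78 to 99% and 28 to 59%. All of this depends on the assumed time courses, correlations, equal weights and SDs. The documents do not give the time course, and the margin is stated inconsistently, which is a separate matter. This should be fixed before analysis.

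**What to change.** In sections 10.1 to 10.3, state that the primary non-inferiority comparison is the treatment difference at week 104, estimated from the repeated-measures model. List weeks 4, 12 and 26 as supportive, matching Table 2, and remove weeks 6 and 52 from the outcome definition.

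This changes wording only and adds no visits or patients. The stated 13 per group, a single-comparison calculation, does not change because of it. The price is precision: the 95% interval is about 14 to 45% wider than for an equally weighted four-visit average, for assumed correlations of 0.7 down to 0.3.
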